9.3.4. Covariates

Table 4. Covariates		
Variable	Role	Operational definition
Age	Patient Characteristics, Subgroup	
The number of years between the index date and the patient birth year. Age will be reported in the following categories: 18-64 and 65+.
 
Continuous statistics including mean, standard deviation (SD), median (Q1-Q3), minimum, and maximum, will also be summarized.
 
Model specification: continuous linear

Sex	Patient Characteristics	
Sex will be reported as Male ('M'), Female ('F'), and Unknown
 
Model specification: categorical

US Geographic Region	Patient Characteristics	
US geographic region will be derived from the patient state and categorized into the following:
 
Northeast – Connecticut, Maine, Massachusetts, New Hampshire, Rhode Island, Vermont, New Jersey, New York, Pennsylvania
 
Midwest – Indiana, Illinois, Michigan, Ohio, Wisconsin, Iowa, Kansas, Minnesota, Missouri, Nebraska, North Dakota, South Dakota
 
South – Delaware, District of Columbia, Florida, Georgia, Maryland, North Carolina, South Carolina, Virginia, West Virginia, Alabama, Kentucky, Mississippi, Tennessee, Arkansas, Louisiana, Oklahoma, Texas
 
West – Arizona, Colorado, Idaho, New Mexico, Montana, Utah, Nevada, Wyoming, Alaska, California, Hawaii, Oregon, Washington
 
Other/unknown – Puerto Rico/unknown region
 
Model specification: categorical

Charleston Comorbidity Index (CCI)	Patient Characteristics	
Charleston Comorbidity Index score will be measured during the 12 month baseline period before index and will be reported in the following categories: 0, 1, and 2+. Continuous statistics including mean, standard deviation (SD), median (Q1-Q3), minimum, and maximum, will also be summarized.
 
Model specification: categorical (0,1,2+)

Prior Pneumonia or respiratory failure	Patient Characteristics	Any code (any setting) within the 1 year baseline for any type of pneumonia or respiratory failure
Prior heart disease	Patient Characteristics	Any code (any setting) within the 1 year baseline for heart disease
Prior asthma	Patient Characteristics	Any code (any setting) within the 1 year baseline for asthma

PFIZER CONFIDENTIAL

Table 4. Covariates

Variable	Role	Operational definition
Prior chronic lung disease	Patient Characteristics	Any code (any setting) within the 1 year baseline for chronic lung disease

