9.5. Study Size

The sample size for this study is fixed by the duration of the observation window. All subjects who meet the inclusion/exclusion criteria will be included in the analyses.

Feasibility analyses from 31 August 2022- 16 January 2023 confirmed the availability of data to identify vaccinated subjects. Table 5 below shows the estimated number of patients in each group.

Table 5. Estimated Number of Patients in Each Vaccination Exposure Group

	Group 1: Same Day	Group 2: COVID- 19 alone	Group 3: Flu alone	CCl [REDACTED]
18-64	244,864	144,695	772,418	CCl [REDACTED]
65+	382,806	225,842	1,351,093	CCl [REDACTED]

Composite COVID-19 hospitalizations/UC/ED

For 65+, and the Group 1 vs Group 2 comparison of the COVID-19 related composite hospitalizations/ED/UC endpoint, we assume the percentage of patients in Group 1 will be 63% and the expected percentage of patients in Group 1 and Group 2 with an event overall will be 0.56%. If we use a non-inferiority margin of 1.15 for the upper bound of the 95% CI, 1-sided alpha of 0.025, and 80% power, and an expected HR of 1, then we would need 1,724 events resulting in 193,548 patients in Group 1, and 113,671 in Group 2, which meets our current estimated sample size.¹⁹

For 18-64, and the Group 1 vs Group 2 comparison of the COVID-related composite hospitalizations/ED/UC endpoint, we assume the percentage of patients in Group 1 will be 63% and the expected percentage of patients in Group 1 and Group 2 with an event overall will be 0.066%. If we use a non-inferiority margin of 1.15 for the upper bound of the 95% CI, 1-sided alpha of 0.025, and 80% power, and an expected HR of 1, then we would need 1,638,003 in Group 1, and 962,002 in Group 2, which does not meet our current estimated sample size.

Composite influenza hospitalizations/UC/ED

For 65+ and for the Group 1 vs Group 3 comparison of the flu-related composite hospitalizations/UC/ED endpoint, we assume the percentage of patients in Group 1 will be 23% and the expected percentage of patients in Group 1 and Group 3 with the endpoint overall will be 0.3%. If we use a non-inferiority margin of 1.15 for the upper bound of the 95% CI, 1-sided alpha of 0.025, and 80% power, and an expected HR of 1, then we would need 2,269 events resulting in 176,179 in Group 1, and 589,817 in Group 3, which meets our current estimated sample size.

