9.7. Data Analysis

There is not a separate Statistical Analysis Plan document for this study. All methodology for summary and statistical analyses of data collected in this study is contained in this section. All computations and generation of tables will be performed using Statistical Analysis System (SAS) version 9.4 or higher (SAS Institute, Cary, NC, US).

All analyses will be conducted for the following age subgroups: 18-64 and 65+.

Descriptive statistics will be presented to describe baseline characteristics by vaccination exposure group. Baseline characteristics will be described by frequency distribution for categorical variables while continuous variables expressed in terms of their mean and standard deviation or median and interquartile range (IQR) as appropriate. In general, missing or unavailable data will not be imputed and data will be analyzed as they are recorded in the database.

To account for imbalance in patient characteristics between the vaccine exposure groups, 2 separate logistic regression models will be used to create a propensity score used to calculate an inverse probability of treatment weights (IPTW). The two models will be as follows: Same day vs COVID-19 alone, and separately Same day vs Flu alone. Weights will be stabilized to avoid exertion of outliers, and we will further evaluate whether there is a need to truncate at the 1st and 99th percentile. Covariate balance before and after weighting will be assessed using standardized mean differences, separately for the same day/COVID-19 alone and Same day/flu alone comparisons. All variables listed in “[Covariates](#)” section with model specification instructions will be included in the score. If there are model convergence issues, changes in model specification may occur (eg, dropping variables with very low prevalence, categories may be collapsed further etc). Variables with residual imbalance will be included in the model for further adjustment.

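### Age enters the propensity scores as one linear term and balance is checked on means only, so curved uptake by age could leave confounding of the severe composites that passes the check

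*Combined protocol and SAP*

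**What the plan says.** Section 9.3.4, Table 4, gives age the instruction "Model specification: continuous linear". For description, "Age will be reported in the following categories: 18-64 and 65"+, with mean, SD, median, quartiles and range.

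Section 9.7 states that "2 separate logistic regression models will be used to create a propensity score": one for Same day against COVID-19 alone, one for Same day against Flu alone. Every Table 4 variable with a model specification enters the score. On diagnostics, "Covariate balance before and after weighting will be assessed using standardized mean differences". No threshold is given, and no variance ratio, age-band or distributional check is named. The remedy is that "Variables with residual imbalance will be included in the model for further adjustment". Non-convergence is the only stated ground for changing a specification, and no sensitivity analysis varies the form of age.

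The same section says "All analyses will be conducted for the following age subgroups: 18-64 and 65"+. It does not say whether the propensity models are refitted within those groups.

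**The concern.** A single linear term in a logistic score makes the weighted groups agree closely on mean age. It does not make them agree on the spread or tails of age. If uptake of same-day vaccination peaks in the middle of an age group and falls at the ends, the weighted groups can have the same mean age and different shares of the very old. Where risk rises exponentially with age, equal means do not give equal risk.

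The SMD then examines the very quantity that the model has just made equal. It may pass, and the rule for adding imbalanced variables may not be triggered. The two reported age categories do not help, because they coincide with the analysis groups and are constant within each.

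What is at stake is a bias of a few percent in the hazard ratio (HR) for the severe composites. That would be minor in many studies. It matters more here because section 9.5 works to a margin of 1.15 and the 65+ comparison is large, so the confidence interval will be narrow relative to the margin.

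**Working it through.** **1. The plan's own figures.** Section 9.5 uses a "non-inferiority margin of 1.15 for the upper bound of the 95% CI, 1-sided alpha of 0.025, and 80% power", with "an expected HR of 1". Required events are d = (1.960 + 0.842)² / [q(1 − q)(ln 1.15)²], where q is the Group 1 share.
- COVID-19 composite, 65+, q = 0.63: 7.849 / (0.2331 × 0.01953) = 1,724 (stated 1,724). Dividing by 0.56% gives 193,950 and 113,907 patients (stated 193,548 and 113,671; within 0.3%).
- Influenza composite, 65+, q = 0.23: 7.849 / (0.1771 × 0.01953) = 2,269 (stated 2,269).

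The sample size reproduces and is not in dispute.

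**2. How steep is risk in age?** Ratios of the section 9.5 rates, 65+ over 18-64:

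| Endpoint | Rates | Ratio |
|---|---|---|
| COVID-19 composite | 0.56% / 0.066% | 8.5 |
| Influenza composite | 0.3% / 0.09% | 3.3 |
| COVID-19 outpatient | 1.77% / 1.47% | 1.2 |
| Influenza outpatient | 0.47% / 0.76% | 0.62 |

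The documents give no mean ages. If the two groups' means are 27 years apart (assumed), the log-hazard slopes are ln(8.48)/27 = 0.079 and ln(3.33)/27 = 0.045 per year for the composites. I use 0.05-0.08.

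**3. Illustration in 65+, score fitted within the group, Group 1 vs Group 2.** This is a deterministic calculation on a one-year age grid, with no vaccine effect. Assumed, not in the documents:
- mean age 72.9, SD 6.8;
- true uptake logit p = a + bz + cz², where z is standardised age, c = −0.05, −0.10 or −0.20, and the overall Group 1 share is 63%;
- hazard proportional to exp(slope × age).

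A logistic score with linear age was fitted, inverse probability weights were applied, and the ratio of weighted mean hazards was taken. Its true value is 1.

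| Group 1 share over age | Weighted age variance ratio | Downward bias, slopes 0.05-0.08 |
|---|---|---|
| 0.59-0.65 | 0.93 | 0.6-1.5% |
| 0.48-0.66 | 0.87 | 1.0-2.9% |
| 0.26-0.68 | 0.77 | 1.7-5.1% |

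The absolute weighted age SMD was at most 0.006 throughout. For Group 1 vs Group 3 the bias was 0.4-5.5% with SMD at most 0.010. Adding a quadratic age term returned the ratio to 1.000 in every scenario.

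**4. One score pooled over all ages, then analysed by group (slope 0.08).** The overall age SMD was at most 0.03. Within 65+ it was −0.09 to −0.32, with null ratios of 0.94 to 0.79. An SMD computed within 65+ could show this.

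**5. Effect on the 1.15 margin, 65+, Group 1 vs Group 2.** Table 5 gives 382,806 + 225,842 = 608,648 patients, and 0.56% of these is about 3,408 events. With q = 382,806 / 608,648 = 0.629, SE(log HR) = 1/√(3,408 × 0.629 × 0.371) = 0.0355, with no allowance for weighting. At a true HR of 1.15 and multiplicative bias B, the chance of declaring non-inferiority is Φ(−1.960 − ln B / 0.0355):
- B = 1: 2.5%
- B = 0.99: 4.7%
- B = 0.97: 13.5%
- B = 0.95: 30.4%

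For bias the other way, at a true HR of 1, power falls from 97.6% to 70.4% when B = 1/0.95.

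**The case against.** The strongest reply is that the bias rests on something the documents do not contain. It needs uptake to be curved in age on the logit scale after conditioning on every other covariate, and no uptake by age within 65+ is given. The score also includes Charlson category, high-risk conditions, nursing home and skilled nursing claims, functional status and prior hospitalization, some of which may absorb curvature; the illustration has age alone. This stands, and it is why the point is conditional.

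Other protections are real but partial. Splitting the analysis at 65 removes the largest age contrast. The planned SD and quartiles of age by exposure group could show different spread, but weighted versions are not promised. The three negative control outcomes (section 9.3.2), including hospitalization in days 1-14, could warn of residual confounding without identifying age as the cause.

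A reader might infer more than the documents support:
- That age is the strongest risk factor for every endpoint. The documents do not say so. Their rates support a steep gradient only for the severe composites, and influenza outpatient visits run the other way.
- That the check can never detect the problem. If the score is pooled across ages, a within-group SMD could.
- That the bias is nearer 8% (null HR 0.92). That needs hazard doubling every 7 years (ln 2 / 7 = 0.099 per year), strong curvature and a substantial share of patients aged 90-95. With slopes of 0.05-0.08, varying the age distribution and the maximum age (89 or 95) gave 0.970-0.996 for a mild curve and 0.944-0.993 for a strong one.

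**Conclusion.** The point holds as a conditional weakness with a nearly free remedy. What is certain from the text is that age has one linear term, that the only named balance check compares means, and that the corrective rule depends on that check. What is assumed is curvature, the age distribution and the within-group risk slope. Under those assumptions the null HR in 65+ is off by about 0.5-5% for a score fitted within the group, downward if uptake is concave in age and upward if convex. Against the 1.15 margin, a downward bias of 1-5% takes false non-inferiority from 2.5% to about 5-30% before any variance inflation from weighting. The documents do not support saying that the estimates will be biased, only that the plan would have no direct way of seeing it if they were. The point bears on the severe composites and has little force for the outpatient endpoints on the plan's own rates. It is a worthwhile improvement, not a flaw that invalidates the design.

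**What to change.** In section 9.7, state that each of the two propensity models is fitted separately within 18-64 and within 65+. In Table 4, replace the linear term for age with a restricted cubic spline (4-5 knots) or 5-year bands. Add to the balance table, for each comparison and age group, the weighted age variance ratio and the weighted proportions in each age band, alongside the SMD.

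The cost is a few degrees of freedom per model. The smallest comparison in Table 5 has 244,864 + 144,695 = 389,559 patients. No new data are needed, and the required events (1,724 and 2,269) do not change.

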Prior diabetes	Patient Characteristics	Any code (any setting) within the 1 year baseline for diabetes
Prior kidney disorders	Patient Characteristics	Any code (any setting) within the 1 year baseline for kidney disorders
Month of index date	Patient Characteristics	August/September, October, November, December, January (Note: August will be combined with September as only 1 day of August will be included in the cohort). Model specification: categorical
Prior Influenza vaccination	Patient Characteristics	One claim (NDC or CPT) for influenza vaccine of any type measured between 31 August 2021 – 31 May 2022 Model specification: dichotomous (yes/no)
COVID-19 vaccination in the 1 year prior	Patient Characteristics	One claim (NCD, CPT, procedures) for COVID vaccine of any type in the 365 days before index separated into the following time periods: 
 Recent vaccination: ≤ 60 days prior to index Older vaccination: Between 61 and 365 days prior to index No evidence of vaccination in the prior year If there is evidence of >1 COVID vaccination in the 365 days prior to index, patients are categorized using the date of the most recent dose administered during the baseline period. Model specification: categorical (3 level)
Time from last COVID-19 vaccine dose (Due to the likelihood of misclassification, this variable will be used for descriptive table only, not for model)	Patient Characteristics	Number of days from last COVID-19 vaccine dose. Reported as categories: ^{17,18} <60 days, 60-179, ≥ 180 , not applicable. Continuous statistics including mean, standard deviation (SD), median (Q1-Q3), minimum, and maximum, among those with a prior dose.
Monovalent mRNA COVID-19 vaccine in the 60 days prior to index (Note for descriptive table only, not for model due to collinearity with covid vaccine in the prior year above)	Patient Characteristics	Yes/No. One claim (NCD, CPT, procedures) for monovalent mRNA COVID-19 vaccine between 01 July 2022 – 30 August 2022

PFIZER CONFIDENTIAL

Table 4. Covariates

Variable	Role	Operational definition

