Type of index influenza vaccine administered (Note for descriptive table only, not for model)	Patient Characteristics	
Categories include: Enhanced/Standard/Unknown, and each specific type of vaccine
 
 • Standard 
 • Egg-based standard dose injection (Afluria, Fluarix, FluLaval, FluZone Standard Dose) • FluZone intradermal • Flucelvax (cell-based) • FluMist • Multiple • Enhanced 
 • FluZone High dose (Enhanced) • Flublok (recombinant/Enhanced) • Fluad (adjuvanted/Enhanced) • Multiple • Unknown 
See below for operational definition for assigning specific flu vaccines.

Concurrent Shingrix vaccination (any dose)	Patient Characteristics	
NDC or CPT code for Shingrix on the same day as the index vaccination
 
Model specification: dichotomous (yes/no)

Prior Shingrix vaccination	Patient Characteristics	
NDC or CPT code for Shingrix in the 365 days prior to index
 
 • 1 prior dose • 2 prior doses (measured on unique days) 
Model specification: dichotomous (yes/no) (Note: number of doses used in descriptive table only)

Concurrent pneumococcal vaccination	Patient Characteristics	
NDC or CPT code for polysaccharide or conjugate pneumonia vaccine on the same day as the index vaccination
 
Model specification: dichotomous (yes/no)

PFIZER CONFIDENTIAL

Table 4. Covariates

Variable	Role	Operational definition
Prior pneumococcal vaccination	Patient Characteristics	NDC or CPT code for polysaccharide or conjugate pneumonia vaccine in the 365 days prior to index Model specification: dichotomous (yes/no)
Vaccine administration setting	Patient Characteristics	Vaccine administration setting will be determined based on the reported place of service for the claim. Prescription claims will be assumed to have occurred in the Pharmacy setting. The most common settings will be reported and patients with multiple conflicting administration setting codes on index will be classified as multiple. Model specification: pharmacy, office, other
Nursing home residence	Patient Characteristics	Any claim with care location (POS =32) of nursing home in the 365 days prior to index. Model specification: dichotomous (yes/no)
Skilled nursing facility	Patient Characteristics	Any claim with care location of SNF (POS = 31) in the 365 days prior to index. Model specification: dichotomous (yes/no)

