9.4. Data Sources

Optum's Clininformatics Data Mart (CDM) comes from a database of administrative health claims for members of a large national managed care company affiliated with Optum. The database includes over 73 million unique lives (2007 through 2021). Clininformatics Data Mart is statistically de-identified under the Expert Determination method consistent with HIPAA and managed according to Optum customer data use agreements. These administrative claims submitted for payment by providers and pharmacies are verified, adjudicated, adjusted, and de-identified prior to inclusion. The Claims data comprises both commercial/employer sponsored plans and Medicare Advantage health plan data. This data covers ~30% of the national Medicare Advantage population. The population is geographically diverse, spanning all 50 states. In addition to medical claims and pharmacy claims, the Claims data includes tables with member eligibility and inpatient confinements. The Claims data also includes standard pricing for all medical claims, pharmacy claims, and inpatient confinements. Mortality is provided as month and year of death and is sourced from Centers for Medicare and Medicaid Services, Social Security Administration Death Master File, facility claims with inpatient death, discontinuation of coverage due to death and external obituary data.

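### Both propensity scores adjust for geography by broad region although region is built from patient state, so any confounding between states within a region would be neither removed nor shown

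*Combined protocol and SAP*

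**What the plan says.** Section 9.3.4, Table 4, defines the only location covariate: "US geographic region will be derived from the patient state and categorized into the following". It has four regions and a fifth level, "Puerto Rico/unknown region", and its modelling instruction is "Model specification: categorical". Counting the lists in Table 4, the regions hold 9 (Northeast), 12 (Midwest), 17 (South, including the District of Columbia) and 13 (West) units, 51 in all. Section 9.4 says of the database: "The population is geographically diverse, spanning all 50 states".

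Section 9.7 sets the rule for the scores: "All variables listed in “[Covariates](#)” section with model specification instructions will be included in the score". State has no such instruction, so it is not used.

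Two related covariates do enter the scores. Index month has the levels "August/September, October, November, December, January", and vaccine administration setting has "Model specification: pharmacy, office, other". No interaction of either with geography is stated.

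Section 9.7 checks balance with standardized mean differences, adds variables with residual imbalance to the model, and then fits ordinary Cox models with no stratification by place. The readable sensitivity analysis only adds censoring at antiviral dispensing. Section 9.9 does not discuss geography.

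**The concern.** Apart from all-cause hospitalization, the effectiveness endpoints are infections counted over a single season, 31 August 2022 to 14 February 2023. How much virus circulates where a patient lives bears directly on the outcome. The sponsor already treats location as a confounder by including region, so the question is resolution. One level, South, runs from Delaware to Texas.

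Confounding within a region needs two things together: states that differ in virus activity, and states that differ in the share of recipients vaccinated on the same day. If both occur, the comparison of Same day with either single-vaccine group picks up the difference in local activity.

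The planned checks would not reveal it. Region can be balanced while the states inside it are not, because state is not a checked variable. Urinary tract infection and accidental injury were chosen to reflect care seeking and would not be expected to follow local COVID-19 or influenza activity. The third negative control, hospitalization in the first 14 days, is all-cause, and Section 9.2.2 excludes patients with a COVID-19 or influenza code in that window.

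**Working it through.** **1. Scale set by the plan's own figures.** For the 65+ COVID-19 composite, Section 9.5 uses a margin of 1.15, one-sided alpha 0.025, 80% power and a 63% Group 1 share. The Schoenfeld formula gives (1.960 + 0.842)² / (0.63 × 0.37 × (ln 1.15)²) = 1,724 events, as stated. This figure is not disputed.

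The Table 5 numbers give (382,806 + 225,842) × 0.0056 ≈ 3,408 expected events, with a Group 1 share of 0.629. Before weighting, SE(log HR) = 1/√(3,408 × 0.629 × 0.371) ≈ 0.035. Weighting would enlarge this somewhat.

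**2. Strongly aligned case (assumed inputs).** Take two equal-sized states in one region and a true HR of 1. Let a and b be their same-day shares, and let k be the infection rate in the second state relative to the first. With adjustment for region only,

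HR = [(a + bk)/(a + b)] / [((1 − a) + (1 − b)k)/(2 − a − b)].

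For example, a = 0.58, b = 0.68, k = 2 gives (1.94/1.26)/(1.06/0.74) = 1.540/1.432 = 1.07.

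| Comparison (overall same-day share) | Shares | k | HR | HR if reversed |
|---|---|---|---|---|
| Same day vs COVID alone (63%) | 60% / 66% | 1.5 | 1.03 | 0.97 |
| | 58% / 68% | 2 | 1.07 | 0.93 |
| | 55% / 71% | 2 | 1.12 | 0.89 |
| Same day vs Flu alone (23%) | 20% / 26% | 1.5 | 1.03 | 0.97 |
| | 18% / 28% | 2 | 1.10 | 0.91 |

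With only two states, share and rate are perfectly aligned. For the overall HR to move this much, the same alignment must hold in every region.

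**3. Unrelated and weakly related cases (assumed inputs).** I simulated 9, 12, 17 and 13 units per region with the same spreads: share SD equal to half the share contrast, and log-rate SD equal to half of ln k. True HR was 1, adjustment was for region only, and state sizes were equal or skewed.

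| Scenario | Mean absolute bias, correlation 0 | HR at correlation 0.3 | HR at correlation 1 |
|---|---|---|---|
| COVID alone, 60/66%, 1.5-fold | 0.3% | 1.01 | 1.02 |
| COVID alone, 58/68%, 2-fold | 0.8–1.0% | 1.02 | 1.06–1.07 |
| COVID alone, 55/71%, 2-fold | 1.3–1.6% | 1.03 | 1.11–1.12 |
| Flu alone, 20/26%, 1.5-fold | 0.4–0.5% | 1.01 | 1.03 |
| Flu alone, 18/28%, 2-fold | 1.1–1.3% | 1.02–1.03 | 1.08–1.09 |

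**4. What a given bias would do.** For the 65+ COVID-19 composite, with SE 0.035 and the 1.15 margin, power at a true HR of 1 is Φ[(ln 1.15 − ln bias)/SE − 1.96]. This is 97.6% with no bias, 87% at 1.03, 73% at 1.05 and 24% at 1.10. In the other direction, the chance of meeting the margin at a true HR of 1.15 is Φ[−ln(bias)/SE − 1.96]: 2.5% with no bias, 14% at 0.97 and 30% at 0.95.

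**5. Feasibility of using state.** The smallest age-specific comparison has 244,864 + 144,695 = 389,559 patients. Its smaller group averages 144,695/51 ≈ 2,840 patients per unit, or about 570 per unit and index month. Events are much scarcer for the 18-64 COVID-19 composite: 389,559 × 0.066% ≈ 257, about 5 per unit.

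**The case against.** The strongest reply is that neither half of the confounding is documented. The plan gives no state-level infection rates and does not say that same-day vaccination varies by state. A reader might infer that confounding is present and biases the results by several percent. The documents do not support that: they show only that state is left out. The larger figures also need share and activity to line up the same way in every region. With no systematic link, the bias is around 1%. This stands, and it limits the claim.

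Second, the scores already contain administration setting and index month, as well as prior COVID-19 and influenza tests and infections, and the formula above lets none of them absorb anything. This stands in part. Month enters as one national term, and setting does not separate one state's pharmacies from another's, so they may reduce the bias but cannot be relied on to remove it.

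Third, the 1.15 margin appears only in the sample-size text. Section 9.7 asks for HRs with 95% CIs and states no non-inferiority decision. Step 4 is therefore a yardstick, not a forecast of a wrong decision.

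Fourth, a reader might infer that the Cox baseline hazard must be stratified by state in the main analysis. That goes too far. It is not needed once state is in the weights, it does not align epidemic waves in calendar time, and some endpoints have too few events.

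Finally, state is not known for every patient, because the fifth level includes unknown region.

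**Conclusion.** The point holds as a gap in control and in checking, not as a demonstrated bias. Region is built from patient state, yet only region enters the scores, and no readable balance check, negative control, outcome model or sensitivity analysis works at state level.

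The size and direction of any confounding cannot be derived from the documents. It is zero if, within each region, either activity or same-day share is equal across states. Under the assumed contrasts it is typically 0.3% to 1.6% on the HR when share and activity are unrelated, about 1% to 3% at a correlation of 0.3, and roughly 3% to 12% when they are strongly aligned across regions. Any of these could be reduced by the covariates already in the scores. For the larger comparisons sampling error is small, so a bias in the upper part of this range would matter for interpretation. Redacted text could not be checked.

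**What to change.** In Table 4, change the modelling instruction for geography so that patient state replaces region in both propensity scores. Keep other/unknown as a level, and merge sparse states with a neighbour in the same region under a rule fixed in advance. Section 9.7 already allows categories to be collapsed if a model does not converge. Report standardized mean differences by state before and after weighting for each comparison. Keep region for the descriptive table.

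As a sensitivity analysis, add state by index month to the scores, or fit a state-stratified Cox model, for the endpoints with enough events. The 18-64 COVID-19 composite, at about 257 expected events, is unlikely to support this.

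Cost: 51 units plus other/unknown need 51 indicator terms against 4 for the five-level region, so at most 47 more per score and fewer after merging. No new data are needed and no stated sample size changes. The downside is somewhat more variable weights, which the planned stabilization and possible truncation already address, and some merging of small states.
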